## The research plan

### 1. Clinical Value of Plasma Humanin in Acute Kidney Injury

#### 1.1 Study design

This study is a single-center cross-sectional study, observed and analyzed patients with acute and chronic kidney disease from August 2022 to June 2024, according to the following criteria: adult patients aged 18 years, both male and female; AKI patients: acute kidney injury patients meeting the definition of KDIGO guidelines; control group: people from healthy examination, with normal blood routine physical examination, urine routine, liver function, renal function, glycosylated hemoglobin; patients had complete baseline medical records, including renal and kidney function, urinary protein level, blood creatinine value; agreed to join the group and signed informed consent;

Population was excluded by the following criteria: patient age <18 years; patient baseline data was missing.

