#### 1.2 Relevant Definitions

According to the 2012 Global prognosis (KDIGO) criteria, acute kidney injury (Acute Kidney Injury, AKI) was defined as: blood creatinine level increased 0.3 mg/dl ( $26.5 \mu\text{mol/L}$ ) or more than 1.5 times or above the base value, and clearly or inferred to occur within 7d; or continuous 6h urine volume  $<0.5\text{ml kg}^{-1} \text{h}^{-1}$ ;

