#### 1.3 Data collection

Observational analysis of patients with acute kidney injury from August 2022 to June 2024 in our hospital, and collected plasma from patients meeting the inclusion criteria and divided into AKI group and control group

Clinical baseline data of patients meeting the inclusion criteria, including gender, age, blood pressure, underlying diseases (hypertension, diabetes, hyperuricemia), serum creatinine, eGFR, serum albumin, hemoglobin concentration, glycated hemoglobin, cholesterol, triglycerides, high-density lipoprotein, low density lipoprotein, uric acid, blood phosphorus, blood calcium, potassium, serum iron, 24h urinary protein / urinary albumin, urinary protein / urinary albumin creatinine ratio.

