### 2. plasma Humanin concentration detection

#### 2.1 Samples to be taken

Patients who met the inclusion criteria were retained for 4ml of blood / sterile urinary urine with an EDTA tube during hospitalization. Within 2h, after centrifugation (3000 r/min, 10min), take the supernatant at 300-600  $\mu$  in the  $-80^{\circ}\text{C}$  refrigerator.

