### 3. Statistical methods

SPSS software. Measurement data following normal distribution are described by ( $\bar{x} \pm s$ ) and t test was used for comparison between groups. Count data are represented by frequency, percentage (%), and chi-square test. The receiver working characteristic curve (ROC) was drawn to analyze the diagnostic value of Humanin for AKI. A P <0.05 was considered as a statistically significant difference.

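### Section 1.1 can remove AKI patients from the Humanin ROC for lacking urinary protein or other baseline data that neither the AKI definition nor the ROC uses

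*Protocol*

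**What the plan says.** Two clauses of protocol section 1.1 act together. The inclusion clause asks that "patients had complete baseline medical records, including renal and kidney function, urinary protein level, blood creatinine value". The exclusion clause reads: "Population was excluded by the following criteria: patient age <18 years; patient baseline data was missing". The exclusion clause does not itself name urinary protein; the inclusion clause does. Neither exempts any variable, and nothing later in the protocol relaxes them.

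Controls have their own entry tests: "control group: people from healthy examination, with normal blood routine physical examination, urine routine, liver function, renal function, glycosylated hemoglobin". A control therefore needs a urine result in any case, so the point concerns AKI patients.

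Section 1.2 defines AKI by serum creatinine ("blood creatinine level increased 0.3 mg/dl", or a relative rise) or by low urine output ("continuous 6h urine volume" below a threshold). Section 1.3 lists urinary protein, in several forms, among the clinical baseline data. Section 3 plans t and chi-square tests between groups and one diagnostic analysis: "The receiver working characteristic curve (ROC) was drawn to analyze the diagnostic value of Humanin for AKI".

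**The concern.** An AKI patient who satisfies section 1.2 and has a Humanin value supplies all that the ROC needs: disease status and marker. Section 1.1 nevertheless shuts that patient out if urinary protein, or another baseline item, is not on record. The ROC then describes AKI patients with complete records, not AKI patients as section 1.2 defines them. If patients with incomplete records differ in Humanin, the AUC is biased for the wider group; if they do not, cases are lost for nothing.

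The protocol itself fixes eligibility, so this is not a detail that can be assumed to sit in an unseen analysis plan. The between-group comparisons in section 3 may use urinary protein, but each can be run in those with data, without removing anyone from the ROC.

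**Working it through.** **Is the item needed?**

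| Step in the protocol | Uses urinary protein? |
|---|---|
| Entry of AKI patients (1.1) | Yes, named in the completeness condition |
| Definition of AKI (1.2) | No: creatinine or urine volume |
| Baseline data (1.3) | Yes, as a descriptor |
| Between-group tests (3) | Possibly, one variable at a time |
| ROC of Humanin for AKI (3) | No, and no multivariable model is stated |

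Urinary protein is thus required at entry, but it plays no part in classifying cases or in the diagnostic analysis.

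**How large could the effect be?** The protocol gives no missingness rate, sample size or expected AUC, so there is no figure of its own to reproduce. All inputs below are assumptions:

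- m, the share of AKI patients lost only through this rule: 1%, 2% or 5%.
- No replacement of those lost (section 1.1 gives a date window and no sample size).
- Humanin normal with equal variance in both groups, and a shift of d = 0.8 standard deviations in the retained cases.

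*Precision.* The case contribution to the variance grows at most by 1/(1 − m), so the interval widens by at most 1/√(1 − m) − 1:

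- m = 0.01: 0.0050
- m = 0.02: 0.0102
- m = 0.05: 0.0260

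With equal groups before the loss, the Hanley-McNeil standard error (AUC 0.714, 100 per group assumed) rises by 0.0033, 0.0067 and 0.0171. With 50 or 200 per group the results agree to about 0.0001.

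*Bias.* AUC = Φ(d/√2), so d = 0, 0.8 and 1.6 give 0.500, 0.714 and 0.871. The AUC is linear in the case distribution:

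AUC(all) = (1 − m) × AUC(kept) + m × AUC(lost)

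Hence reported minus full = m × (AUC(kept) − AUC(lost)):

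| m | Lost cases: no shift | Same shift | Twice the shift |
|---|---|---|---|
| 1% | +0.0021 | 0 | −0.0016 |
| 2% | +0.0043 | 0 | −0.0031 |
| 5% | +0.0107 | 0 | −0.0078 |

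Check at 5%: 0.05 × (0.714 − 0.500) = 0.0107, and 0.05 × (0.714 − 0.871) = −0.0078.

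*Sensitivity to the assumed loss.* At m = 10% to 30% the same formula gives +0.021 to +0.064 with no shift, −0.016 to −0.047 with twice the shift, and zero with the same shift. Nothing in the documents favours either range of m.

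**The case against.** The strongest reply is that this is an ordinary design choice. An eligibility item need not appear in the case definition or in the ROC, urinary protein has a declared use as a baseline descriptor, and the protocol does not contradict itself here. That is fair as to contradiction. It does not show that the diagnostic analysis gains anything from the restriction.

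Second, the rule may exclude hardly anyone. Section 1.1 asks only for a urinary protein level and does not say that it must be quantified, so a urine-routine result might satisfy it. This stands, and it is a reason to call the point minor. It does not help with other missing items, since the exclusion clause names no exception.

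Third, the size rests wholly on assumed missingness, and no mechanism linking incomplete records to Humanin is documented. This also stands.

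Two stronger readings are tempting:

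- A reader might infer that the AUC is biased in a known direction. The documents give neither the missingness nor the Humanin values of those excluded, so neither sign nor size follows.
- A reader might infer that excluded patients have no plasma and can never be restored. Section 1.3 says that the study "collected plasma from patients meeting the inclusion criteria and divided into AKI group and control group", and section 2.1 says: "Patients who met the inclusion criteria were retained for 4ml of blood". These tie sampling to eligibility, but section 2.1 places it during the hospital stay, and no section says whether completeness is checked before or after blood is drawn. Some of those excluded may have a stored sample.

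**Conclusion.** The point holds as a minor one. Section 1.1 allows AKI patients who meet section 1.2 to be dropped from the Humanin ROC for lacking data that neither the definition nor the ROC uses. This is an avoidable selection of cases by record completeness. It is not an internal contradiction, and no bias has been demonstrated.

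If few patients are affected the consequence is small: at an assumed 5% loss, about 1.7% on the width of the interval with equal groups and about 0.01 on the AUC, even when the lost cases show no Humanin shift. If the loss were much larger the AUC could move by several hundredths, but only if lost and retained cases also differed in Humanin. The actual loss cannot be derived from the document, which is why exclusions should be counted and reported.

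**What to change.** In section 1.1, for AKI patients, limit the completeness condition in both the inclusion and the exclusion clause to the data needed to establish AKI under section 1.2. Keep the existing creatinine and renal function requirement, so that patients who qualify by urine volume must still have it. Leave the control criteria and consent unchanged.

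Then:

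- keep in the ROC those AKI patients who have a Humanin value and lack only urinary protein or other descriptive baseline items;
- compare each baseline variable in those with data, showing the denominator;
- report, by group, the number excluded for missing data.

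The window in section 1.1 ends in June 2024. If enrolment is complete, include those excluded only for such items who have consent and a stored sample. Those without a sample cannot be recovered, and for them the count is what can be offered.

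The cost is a change of wording, with no new procedure. The downside is that denominators in the baseline table vary by row.

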#### 1.2 Relevant Definitions

According to the 2012 Global prognosis (KDIGO) criteria, acute kidney injury (Acute Kidney Injury, AKI) was defined as: blood creatinine level increased 0.3 mg/dl ( $26.5 \mu\text{mol/L}$ ) or more than 1.5 times or above the base value, and clearly or inferred to occur within 7d; or continuous 6h urine volume  $<0.5\text{ml kg}^{-1} \text{h}^{-1}$ ;

#### 1.3 Data collection

Observational analysis of patients with acute kidney injury from August 2022 to June 2024 in our hospital, and collected plasma from patients meeting the inclusion criteria and divided into AKI group and control group

Clinical baseline data of patients meeting the inclusion criteria, including gender, age, blood pressure, underlying diseases (hypertension, diabetes, hyperuricemia), serum creatinine, eGFR, serum albumin, hemoglobin concentration, glycated hemoglobin, cholesterol, triglycerides, high-density lipoprotein, low density lipoprotein, uric acid, blood phosphorus, blood calcium, potassium, serum iron, 24h urinary protein / urinary albumin, urinary protein / urinary albumin creatinine ratio.

### 2. plasma Humanin concentration detection

#### 2.1 Samples to be taken

Patients who met the inclusion criteria were retained for 4ml of blood / sterile urinary urine with an EDTA tube during hospitalization. Within 2h, after centrifugation (3000 r/min, 10min), take the supernatant at 300-600  $\mu$  in the  $-80^{\circ}\text{C}$  refrigerator.

#### 2.2 Experimental reagent consumables and instruments

Human humanin peptide (MT-RNR 2) ELISA kit, centrifuge, EP tube, different specifications of enzyme-free gun head, different specifications of pipette gun and exhaust gun, plasma water, microplate reader,  $4^{\circ}\text{C}$  refrigerator,  $-20^{\circ}\text{C}$  refrigerator,  $-80^{\circ}\text{C}$  refrigerator,  $37^{\circ}\text{C}$  incubator, etc

#### 2.3 Experimental method

---

(1) Reagent reheating: Transfer all reagents to room temperature (18-25C) to equilibrate for at least 30 minutes

(2) Reagent equipped with:

- ① Standard: Remove a standard from the kit at 6000-10000rpm for 30 seconds. Dissolve with 1ml sample dilution, pump the gun at the bottom of the cold storage tube for 5 times to dissolve the standard S7; reserve 71.5ml centrifuge tubes with different concentrations (use the following concentrations: 1800,900,450,225,112.5,56.25,28,0 pg / ml);
  - ② Washing liquid working liquid: the concentrated washing liquid should be diluted by 1:25 times with de-ionized water, and qualified before use;
  - ③ Biotin-labeled antibody working solution: biotin-labeled antibody solution is diluted 1:100 times and consummated within 10 minutes before use;
  - ④ Horseradish peroxidase labeled avidin working solution: horseradish peroxidase labeled avidin by 1; 100 times with horseradish peroxidase labeled avidin dilution, within 10 minutes before use;
  - ⑤ Sample dilution: Samples are diluted 1:5 times for testing;
- (3) Add samples: set up standard holes and sample holes to be tested respectively. Add 100u1 to each well, shake the well gently, and warm 37C for 2 hours.
- (4) Leave the liquid and dry without washing.
- (5) 100u1, covered with new plates, and incubated at 37C for 1 hour.
- (6) Remove the liquid in the hole, throw it on, and wash the plate for 3 times. Soak for 2 minutes, 200u / each well and dry.
- (7) Horseradish peroxidase-labeled avidin working solution was 100u1 per well, covered with new plate paste and incubated at 37° C for 1 hour.
- (8) Remove the liquid in the hole, shake it dry, and wash the plate for 5 times. Soak for 2 minutes, 200ul / per well and dry.
- (9) Add substrate solution 90u1,37C for 15-30 min.
- (10) The reaction was terminated by adding 50u1 of the termination solution per well.
- (11) The optical density (OD) of each well was measured at 450nm within 5 minutes of the reaction
- (12) Calculated concentration: According to the standard concentration and the corresponding OD value, the standard curve of Humanin is analyzed by Curve Expert 1.4 software, and the concentration of Humanin to be measured in the sample is calculated by using the equation of the standard curve.

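### Does the Humanin calculation leave out the 1:5 sample dilution, so that reported levels would be five-fold too low?

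*Protocol*

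**What the plan says.** All of the assay wording is in protocol section 2.3, Experimental method.

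- Sample preparation, step (2) item 5: "Samples are diluted 1:5 times for testing". The volumes of plasma and diluent are not given.
- Standards, step (2) item 1: the stock is made up by the instruction "Dissolve with 1ml sample dilution", and the series is then fixed as "use the following concentrations: 1800,900,450,225,112.5,56.25,28,0 pg / ml".
- Loading, step (3): "Add 100u1 to each well", for standards and samples alike.
- Calculation, step (12): after the curve is fitted, "the concentration of Humanin to be measured in the sample is calculated by using the equation of the standard curve". This is the final step.

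Protocol section 3, Statistical methods, uses the resulting values in two ways. For normally distributed measurements, reported as mean and SD, a "t test was used for comparison between groups". A ROC curve "was drawn to analyze the diagnostic value of Humanin for AKI". No Humanin level, threshold or worked sample calculation appears anywhere in the protocol.

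**The concern.** A standard curve converts the optical density of a well into the concentration in that well. The sample wells hold diluted plasma, while the standards carry their nominal concentrations. Nothing in the written procedure offsets the dilution: the standards are not labelled at five times their content, and the loading volume is the same for both. A reader who stops at step (12) would therefore report the concentration in diluted plasma as if it were the plasma concentration.

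Two results would suffer: the descriptive means and SDs, and any numeric cut-off taken from the ROC curve. A threshold on the diluted scale, applied elsewhere to properly back-calculated plasma values, would misclassify people. The dilution notation is also loose, since 1:5 can be read as one part in five or as one part plus five.

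**Working it through.** The protocol gives no Humanin result, so there is no stated figure to reproduce. The only numeric series is the set of standards, and it is consistent.

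**Standards.** Halving from the top, 1800/2^i for i = 0 to 6 gives 1800, 900, 450, 225, 112.5, 56.25 and 28.125. The protocol lists the same values with the last rounded to 28, plus a zero standard.

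**Size of the effect if the correction were omitted.** Plasma concentration = curve reading × dilution factor k.

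| Reading of 1:5 | k | Uncorrected value as share of true | Shortfall | Plasma equivalent of the 28–1800 pg/ml curve |
|---|---|---|---|---|
| One part in five | 5 | 1/5 = 20% | 80% | 28 × 5 = 140 to 1800 × 5 = 9000 pg/ml |
| One part plus five | 6 | 1/6 = 16.7% | 83.3% | 28 × 6 = 168 to 1800 × 6 = 10800 pg/ml |

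If the correction is made but with the other reading of the notation, the error is a factor of 6/5 = 1.2 or 5/6 = 0.83.

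**Effect on the planned analyses.** Multiply every value by the same k.

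- t test: t = (mean₁ − mean₂) / [s_p √(1/n₁ + 1/n₂)]. The mean difference and the pooled SD s_p are both multiplied by k, so k cancels. The statistic and P value do not change.
- ROC: the curve depends only on the ordering of the values, and multiplying by a positive constant keeps the order. The area, and the sensitivity and specificity at each operating point, do not change.
- Cut-off: a threshold c becomes k × c and classifies the same people.

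**Numerical confirmation on assumed data.** These inputs are not from the protocol: 60 people per group, drawn from normal distributions with means 300 and 360 and SDs 80 and 90 pg/ml. The cut-off is the point that maximises sensitivity + specificity − 1.

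| k | t | P | AUC | Sensitivity | Specificity | Cut-off (pg/ml) |
|---|---|---|---|---|---|---|
| 1 | −4.467 | 1.83 × 10⁻⁵ | 0.7317 | 0.617 | 0.80 | 348.7 |
| 5 | −4.467 | 1.83 × 10⁻⁵ | 0.7317 | 0.617 | 0.80 | 1743.5 |
| 6 | −4.467 | 1.83 × 10⁻⁵ | 0.7317 | 0.617 | 0.80 | 2092.2 |

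Only the last column moves, and it moves by exactly k.

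**What step (12) claims.** Its stated target is the concentration in the sample, reached by means of the curve equation. It does not say that the curve value is reported uncorrected. The text supports the statement that the multiplication is not written down. It does not support the statement that the multiplication will be left out.

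**The case for a change.** The best case for a change is that section 2.3 is a bench-level procedure. It gives wash counts, soak times, reagent dilutions and the version of the curve-fitting software, and it states both the dilution and the calculation. In text that detailed, a missing final multiplication is more than a matter left for elsewhere, and an assay formula would not normally be deferred to a statistical analysis plan. The heading of section 2 makes plasma concentration the intended quantity. One added sentence would remove the doubt at almost no cost.

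Part of this stands. The multiplication is unwritten, the notation is not defined by volumes, and a published cut-off would need its scale to be clear. But the section is uneven: step (5) gives a volume without naming the reagent. A gap in such text is weak evidence of what the laboratory does. Whoever prepares the dilution knows the volumes used and so knows whether the factor is 5 or 6.

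A second point is that the cancellation holds only while every sample shares one dilution. If some wells were re-run at another dilution and left uncorrected, values within the study would no longer be comparable. That is true, but the protocol specifies a single dilution for all samples and no re-runs. A laboratory that did use a second dilution could not pool the results without applying the factor.

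A reportable plasma range and re-assay rules are a separate matter. The lowest and highest standards are not shown to be validated quantification limits, so the missing dilution factor gives no ground for declaring one.

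**Conclusion.** The text does omit the back-multiplication, and the range arithmetic is right, but the plan does not need to change. Without the correction, absolute levels and any cut-off would be 80% too low (83.3% under the six-fold reading). The protocol does not say that it is left out, and a laboratory reading diluted samples off a standard curve would apply it as a matter of course. No stated Humanin figure is wrong. The conclusions the study is designed to draw, the group comparison and diagnostic performance, are the same at any common factor.

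This rests on two assumptions: that all samples are run at the one dilution stated, and that the laboratory follows ordinary practice in converting curve readings to plasma values. If the second failed, the damage would be confined to the descriptive levels and the numeric threshold, and one multiplication in the data file would repair it.

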### 3. Statistical methods

SPSS software. Measurement data following normal distribution are described by ( $\bar{x} \pm s$ ) and t test was used for comparison between groups. Count data are represented by frequency, percentage (%), and chi-square test. The receiver working characteristic curve (ROC) was drawn to analyze the diagnostic value of Humanin for AKI. A P <0.05 was considered as a statistically significant difference.

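### The ROC can only separate AKI patients from screened-healthy people, so its stated aim of showing diagnostic value for AKI should be narrowed to that contrast

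*Protocol*

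**What the plan says.** Section 3 of the protocol sets the aim of the ROC analysis and names no comparator: "The receiver working characteristic curve (ROC) was drawn to analyze the diagnostic value of Humanin for AKI". The heading of section 1 is similarly broad: "Clinical Value of Plasma Humanin in Acute Kidney Injury".

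Section 1.1 defines the non-cases: "control group: people from healthy examination, with normal blood routine physical examination, urine routine, liver function, renal function, glycosylated hemoglobin". The cases are adults who meet the KDIGO definition in section 1.2, under which AKI "was defined as: blood creatinine level increased 0.3 mg/dl" or by a relative creatinine rise, or by low urine volume. The only exclusions are these: "Population was excluded by the following criteria: patient age <18 years; patient baseline data was missing". Section 1.3 splits the participants into an AKI group and a control group and describes no third group.

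On who was studied, section 1.1 says the study "observed and analyzed patients with acute and chronic kidney disease from August 2022 to June 2024", whereas section 1.3 has "Observational analysis of patients with acute kidney injury from August 2022 to June 2024 in our hospital". Chronic kidney disease has no inclusion criterion and no group anywhere in the protocol.

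**The concern.** A marker's diagnostic value for AKI is its ability to tell AKI from its absence among patients in whom the question arises. This ROC takes its specificity entirely from people selected for being healthy. They differ from the cases in more than AKI: they must have normal liver function, blood count and glycated haemoglobin, while the AKI patients face no such screen. A difference in Humanin between the groups could reflect AKI, other disease or illness in general, and this ROC cannot tell these apart.

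What is at stake is how the result is read. Under the present wording, a reader could carry the AUC, the specificity or a cut-off over to patients with suspected AKI, whom the study did not sample. The ROC is the only analysis in section 3 that addresses diagnostic accuracy, so the limit applies to the whole of that claim.

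**Working it through.** The protocol states no AUC, cut-off or Humanin value, so there is no figure of its own to reproduce. The check sets the group definitions against the ROC aim. An illustration on assumed inputs follows.

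**Step 1. Who is in the ROC (sections 1.1 and 1.3).**

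- Groups defined: 2 (AKI, control).
- Groups containing patients in whom AKI was considered and ruled out: 0.

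**Step 2. How the controls were screened (section 1.1) against how AKI is defined (section 1.2).**

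| Control screen | Bears on the AKI definition (creatinine, urine volume)? |
|---|---|
| Renal function | Yes |
| Urine routine | Arguably |
| Blood routine | No |
| Liver function | No |
| Glycated haemoglobin | No |

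At least 3 of the 5 screens remove conditions other than AKI, and they do so from the control side only. The AKI side is limited only by age and by completeness of baseline data. This count shows that the groups differ in selection. It does not show that Humanin varies with the screened conditions.

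**Step 3. Does the AUC against healthy people fix the AUC against non-AKI patients? (All inputs assumed.)**

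Assume Humanin, or a transform of it, is normal with equal SD in all populations. Let *d* be the AKI-minus-healthy difference in SD units. Let *s* be the share of that difference also present in non-AKI patients. Nothing in the protocol informs *s*. A negative value means non-AKI patients lie on the other side of healthy people from AKI patients.

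- z = Φ⁻¹(AUC against healthy), and d = √2 · z
- AUC against non-AKI patients = Φ((1 − s) · z)
- Cut-off with 90% specificity in healthy people: 1.2816 SD from the healthy mean, in the direction of AKI
- Specificity of that cut-off in non-AKI patients = Φ(1.2816 − s · d)
- Sensitivity = 1 − Φ(1.2816 − d), which does not depend on s

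For an AUC of 0.80 against healthy, z = 0.8416 and d = 1.190. At s = 0.5 the AUC is Φ(0.5 × 0.8416) = Φ(0.421) = 0.663, and the specificity is Φ(1.2816 − 0.595) = Φ(0.687) = 0.754. The other entries follow in the same way; for an AUC of 0.90, d = 1.812.

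| AUC vs healthy | s | AUC vs non-AKI | Specificity vs non-AKI | Sensitivity |
|---|---|---|---|---|
| 0.80 | −0.5 | 0.897 | 0.970 | 0.464 |
| 0.80 | 0 | 0.800 | 0.900 | 0.464 |
| 0.80 | +0.5 | 0.663 | 0.754 | 0.464 |
| 0.90 | −0.5 | 0.973 | 0.986 | 0.702 |
| 0.90 | 0 | 0.900 | 0.900 | 0.702 |
| 0.90 | +0.5 | 0.739 | 0.646 | 0.702 |

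Under this model the two AUCs agree only when s = 0, and the study as described has no data from which to estimate s. The table shows that the AUC the study can estimate does not determine the one its aim implies. It does not show that the study's AUC will be too high.

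**The case against.** The strongest reply is that section 3 states a purpose and draws no conclusion. It gives no cut-off, no intended-use population and no claim about suspected AKI. The control group is disclosed openly in section 1.1, so a careful reader already knows what the ROC contrasts. With the effect unknown and possibly nil, the remedy comes down to a narrower phrase. The chronic kidney disease wording in section 1.1 might also point to a further group, in which case saying the ROC has only healthy controls would be too strong.

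Parts of this stand:

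- The harm depends on later reporting, which the protocol does not show.
- The illustration rests wholly on assumed inputs and cannot set how serious the point is.
- The comorbidity contrast should not be pushed too far. Section 1.3 records hypertension, diabetes and hyperuricaemia for everyone who meets the inclusion criteria, and no control screen names blood pressure. Among those three, only the glycated haemoglobin screen clearly separates the groups.
- The section 1 heading is a title and makes no accuracy claim of its own.

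The main point is not answered. Disclosing the controls in section 1.1 does not make the aim in section 3 one that those controls can support. The chronic disease phrase supplies no comparator, because no such group is defined and section 1.3 divides participants into AKI and control only. No analysis plan was at hand, but one could not add a comparator that was not enrolled.

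**Conclusion.** The concern holds, with high confidence. As written, section 3 gives the ROC an aim the design cannot meet. It can estimate discrimination of AKI patients from screened-healthy people, and nothing in the protocol extends that to patients in whom AKI is in question.

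The size, as far as the document allows, is two groups, neither of which contains ruled-out AKI, and at least three of five control screens unrelated to the AKI definition. The effect on AUC or specificity cannot be derived and may be nil or go either way. The conclusion rests on the two-group reading of sections 1.1 and 1.3 and needs none of the binormal assumptions. The AKI-versus-healthy comparison is sound as a first step; the fault lies in the scope claimed for it. It should be corrected because the correction changes what the study may conclude.

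**What to change.** 1. **Restate the aim (requested).** In section 3, give the ROC aim as discrimination between AKI patients and healthy people, and limit conclusions and any reported cut-off to that contrast. Apply the same limit wherever section 1 carries the diagnostic claim. This costs wording only; the downside is a narrower claim.

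2. **Add a clinical comparator (only if the material already exists).** This requires stored plasma, signed consent, complete baseline records and documented exclusion of AKI by the section 1.2 criteria in hospitalised patients in whom AKI was considered. If all of these are held, define that group in sections 1.1 and 1.3, report AKI against it as the diagnostic ROC, and keep AKI against healthy as secondary. The cost is extra ELISA wells and one more ROC, whose AUC may be less favourable. A group with chronic kidney disease but no AKI, if held, should be reported as discrimination from chronic kidney disease and not as diagnostic value. If the material does not exist, this step would mean new recruitment and is not requested.

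3. **Reconcile the population wording (separate and minor).** State whether the mention of chronic kidney disease in section 1.1 means AKI patients with underlying chronic disease, whom the exclusions do not remove, or a separate group that must then be defined, or should be deleted. Make section 1.3 agree. This costs wording only.
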